3.1.1.1 BMS-986183 Dose Escalation (Part 1)

In BMS-986183 dose escalation (Part 1), BMS-986183 monotherapy will be administered Q3W (21 days/cycle), and BMS-986183 dose expansion (Part 2) may be initiated once the MTD or a tolerated dose below the MTD for BMS-986183 dose escalation (Part 1) is established.

BMS-986183 Dose Escalation (Part 1): (BMS-986183 administered every 3 weeks)

Approximately 30 subjects will be enrolled in ascending dose level cohorts starting with a flat dose of 3 mg (0.05 mg/kg based on a 60 kg body weight individual) of BMS-986183 monotherapy. BMS-986183 monotherapy will be administered Q3W in a 21-day cycle. The approach for selection of the next dose at each escalation step is presented below. For the rules for escalation decision based on DLT criteria, see Section 4.5.1.

BMS-986183 Dose Escalation (Part 1): Selection of Doses

BMS-986183 dose escalation (Part 1) will be conducted using an mTPI design. The decision governing when to escalate will follow the mTPI algorithm based on incidence of DLTs (Figure 3.1.1.1-1). The decision on what increment to increase the dose is based on DLTs, AEs, and PK and is explicitly described in Figure 3.1.1.1-2. In the mTPI design 1 to 2 subjects will be enrolled in each dose level cohort (up to 3 cohorts) until the first DLT is observed. Once the first DLT is observed or after the first 3 dose level cohorts with no DLT observed, then at least 3 subjects will be enrolled in each subsequent dose level cohort (including the current cohort).

The first dose level cohort will receive a starting dose of 3 mg (0.05 mg/kg based on a 60 kg body weight individual). This dose may produce ADC exposures below those projected for the human efficacious dose range for BMS-986183 (ie, 0.12 to 3.9 mg/kg and an ADC $AUC_{(0-\infty)} = 189$ to 7,804 µg•h/mL). In addition, in the event that target-mediated drug disposition is observed for this compound, ADC exposures may be even lower than these target exposures. Therefore, dose escalation for each subsequent cohort of subjects will be guided first by the incidence of DLTs/AEs as graded by National Cancer Institute (NCI) Common Terminology Criteria for Adverse Events (CTCAE) version 4.03 (NCI CTCAE v4.03) in the first 3 weeks of dosing (DLT evaluation period) and then by available ADC exposure data.

Dose escalations based upon ADC exposure data:

In the absence of DLTs or AEs at the starting dose and in the initial dose level cohorts (1 to 2 subjects in the first 3 cohorts; at least 3 subjects in cohort 4 and subsequent cohorts), ADC exposure data will be used to guide dose escalations up to a maximum of 3-fold as long as exposures fall well below the safety margin (ie, active ADC $AUC_{(0-168h)} = 842 \ \mu g \cdot h/mL$)

determined for the HNSTD (1 mg/kg from the repeat-dose monkey toxicology study). A Bayesian model relating ADC exposure to dose will be derived to guide the next dose level selection. The prior information for the model is based upon target exposures derived from preclinical data (see Appendix 3 and Section 1.1.5.1 for details). Probabilities of ADC exposure at the next dose level will be calculated based upon both the prior information and actual PK data collected in the clinical study. The following criteria will be used to decide if the next dose level can be increased up to a maximum of 3-fold but within the safety margin: 1) the 90% quantile of the predicted next dose level exposure is less than the safety margin; 2) the 90% quantile of the predicted next dose level exposure is less than the target exposure; 3) the next dose level is no more than a 3-fold increase from the current dose level. The first criterion ensures with 90% probability that the next dose level exposures fall below the safety margin. In addition, a CV of 30% will be incorporated into the Bayesian model to ensure that as the dose levels increase, the distribution of next dose level exposures becomes wider and more likely to cover the safety margin, therefore making it less likely to allow dose escalations up to a maximum of 3-fold at higher doses. Once the next dose level exposures are near the safety margin or there is a first occurrence of DLTs/AEs, 3-fold increments will cease and further dose escalations will be based upon mTPI and modified Fibonacci as described previously. Of note, in the absence of DLTs or AEs at the starting dose and in the initial dose level cohorts and in the event that ADC exposure data are not available (e.g. samples weren't drawn at the site or there are significant delays in sample shipping) the next dose level will be a 2-fold increase from the current dose level. See Figure 3.1.1.1-2 for a summary of the decision rules for choice of dose-escalation increments, including use of PK. More details and operating simulation results illustrating the Bayesian model approach are provided in Appendix 3.

Intermediate doses may also be evaluated by safety, PK, and pharmacodynamic if agreed upon by the Sponsor/medical monitor and investigators. If there are dose levels with insufficient data to characterize BMS-986183 monotherapy PK, additional subjects may be enrolled at that dose level upon agreement of the Sponsor/medical monitor and investigators.

Dose escalations based on incidence of DLTs/AEs:

In the absence of ADC exposure data or if the exposure does not fall below the limits described above, initial dose escalations will be in increments of up to 2-fold until the first occurrence of any of the following:

- DLT
- \geq Grade 3 decrease in neutrophil count lasting > 72 hours
- \geq Grade 3 thrombocytopenia lasting > 72 hours

Two subjects with similar \geq Grade 2 AEs that are considered related to BMS-986183 in a single dose level cohort, with the following exceptions: asymptomatic electrolyte abnormalities that can be managed with appropriate supplements and Grade 2 alopecia, fatigue, or nausea (Grade 2 fatigue or nausea that is less than 2 grades from baseline [ie, from Grade 1 to Grade 2] will not trigger a Fibonacci sequence). If 1 or more of the above occur, a modified Fibonacci dose escalation based upon DLTs will be employed for any subsequent dose escalations, and the next immediate escalation increment will be a maximum of 67% of the current dose followed by

increments of 50%, 40%, and 33% respectively for each subsequent dose escalation. If the mTPI algorithm indicates that escalation should continue beyond the first 33% increase, any further dose escalations will be in increments of 33% of the current dose.

In the absence of DLTS or AEs, in the initial four dose levels during dose escalation, then dose escalation will proceed as above. A modified Fibonacci based escalation will be triggered after dose level 4 and no further 2 fold increase in dose will be employed thereafter.

BMS-986183 Dose Escalation (Part 1): Dose Escalation Decision Rules

Enrollment in dose escalation and selection of the MTD will adhere to an mTPI design. The mTPI design provides a simple algorithm for decisions on escalation, expanding at the same dose, and de-escalation, depending on the number of observed toxicities after each dose level cohort (see Figure 3.1.1.1-1). The mTPI method utilizes a target toxicity (DLT) rate and equivalence interval (EI) to make decisions on escalation after each cohort and to estimate the MTD. For this study the target DLT rate is 27% and the EI is 25% to 29%.

Dose escalation will begin at a dose of 3 mg flat dose (0.05 mg/kg based on a 60 kg body weight individual; dose level 1) and will be guided by the cumulative number of subjects who are DLT-evaluable and who experience a DLT. An initial cohort of 1 to 2 subjects will be enrolled sequentially to dose level cohorts 1 to 3 in BMS-986183 dose escalation (Part 1) (as long as no DLTs are observed or criteria above for transitioning from 2-fold increment to modified Fibonacci criteria are **not** met). If a DLT is observed or at dose level cohort 4, the design requires at least 3 subjects per cohort (including the current cohort). A fourth subject may be enrolled in that initial cohort following agreement between the investigator and the Sponsor/medical monitor if the subject is able to start the first day of dosing within approximately 1 week of the third subject in the same dose-escalation cohort. At any dose level, if decision of the mTPI design is to expand the same dose level is specified by the mTPI algorithm when there are already at least 13 DLT evaluable subjects treated at the same dose level or the total of all treated DLT evaluable subjects reaches 30, the dose escalation will be stopped.

Decisions to escalate, add more subjects to the current dose, de-escalate, or de-escalate and declare the current dose as unacceptable (exceeding the MTD) will be based on the rate of DLTs in evaluable subjects within the 21-day DLT evaluation period for BMS-986183 dose escalation (Part 1) (Figure 3.1.1.1-1, and Appendix 1). Subjects with insufficient data to establish safety during the DLT evaluation period at the dose tested may be replaced upon agreement of the Sponsor/medical monitor and investigators.

There will be no intra-subject dose escalation of BMS-986183 monotherapy.

Figure 3.1.1.1-1 shows examples of scenarios guiding decision making that may be encountered during dose escalation with respect to the number of DLT evaluable subjects and the number of subjects with a DLT. All potential combinations of the number of DLTs and number of treated subjects evaluable for DLT are shown in Appendix 1. In addition to escalation or expansion decisions, dose re-escalation is permitted as per Figure 3.1.1.1-1 and Appendix 1 after a decision

to de-escalate is made, except when a dose has been identified as exceeding the MTD. Therefore, a dose level could be revisited multiple times under the mTPI design.

Figure 3.1.1.1-1: BMS-986183 Dose Escalation (Part 1) Algorithm

- ^a Dose level cohorts 1 to 3: Treat 1 to 2 subjects initially if no DLTs and criteria for transitioning from 2-fold increment to modified Fibonacci are not met; after DLT is observed or dose level cohort 4 and on: Treat 3 to 4 subjects initially in that cohort and subsequent.
- ^b At the same dose, n = cumulative number of DLT evaluable subjects, k= cumulative number of subjects who experienced DLT. Decision making based on other combinations of k/n are shown in Appendix 1.
- ^c Treat the next cohort of subjects at the next higher dose
- d Treat 3 to 4 more subjects at the current dose
- ^e Treat 3 to 4 more subjects at the next lower dose
- ^f Unacceptable current dose. Do not re-escalate to this dose.

Figure 3.1.1.1-2:Decision Tree for BMS-986183 Dose Escalation (Part 1) Increments in
Starting and Initial Dose Cohorts

BMS-986183 Dose Escalation (Part 1): MTD Determination

At the end of dose escalation, the MTD will be selected as the dose with the smaller difference of estimated toxicity and the target DLT rate (27%), among the doses used, with isotonic regression modeling of the accumulated DLT data based on the mTPI design.

Once the safety (during DLT evaluation) of a dose level has been established (BMS-986183 dose escalation [Part 1]), additional subjects may be added at that dose to better characterize the PK, safety, and pharmacodynamic profile or to satisfy regional/local requirements (eg, in Chinese subjects where weight or genetic factors may play a role in safety, PK, and pharmacodynamics).

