An informative prior is chosen for the slope B because of limited data in the first few cohorts. Also relevant in the decision rules is the safety margin derived from the repeat-dose monkey study (Section 1.1.5.1 in the protocol). The highest nonseverely toxic dose from that study is 1 mg/kg with an area under the concentration-time curve from 0 to 168 hours of 842 μ g•h/mL. Then, after updating the Bayesian model with the observed data to date and assuming no dose-limiting toxicities or relevant adverse events are observed to date, the following criteria for the next dose will be used to decide if the dose can be increased beyond the default 2-fold increase:

2) Posterior probability of next dose exposure > safety margin is less than 10%, AND

90% quantile of posterior next dose exposure < target exposure, AND

Next dose is \leq 3-fold increase from the current dose

If 2) holds for a dose that is beyond the default 2-fold increase, then that dose may be chosen for the next dose cohort; otherwise, the next dose will default to 2-fold increase.

Simulations were conducted to understand the operating characteristics of the PK-guided dose escalation algorithm. Two scenarios were considered: 1) exposures at each dose match the target exposures (79 μ g•h/mL at the starting dose of 0.05 mg/kg, and then 2-fold increases in dose and

exposure), and 2) exposures at each dose are lower than expected, specifically one-half the level of the target exposures. See Figure 1.

Software for the Bayesian model was written in R v3.2.2 and OpenBugs v3.2.3. Markov chain Monte Carlo was used to fit the model. Twenty simulated trials were generated. Under Scenario 1

Scenarios

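### Part 1 gives two different maximum dose increments when predicted exposure fails the safety-margin criterion and no DLT or listed AE has occurred (before the dose-level-4 cap)

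*Protocol*

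**What the plan says.** Section 3.1.1.1 has separate subsections for exposure-guided and toxicity-guided increments in Part 1.

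- **Exposure subsection.** With no DLTs or AEs, "ADC exposure data will be used to guide dose escalations up to a maximum of 3-fold", provided that exposure stays well below 842 µg•h/mL, the active-ADC AUC(0-168h) at the monkey HNSTD. The 90% quantile of predicted next-dose exposure must lie below that margin. It then names two alternative triggers, predicted exposures near the margin or a first DLT/AE, and says what follows: "3-fold increments will cease and further dose escalations will be based upon mTPI and modified Fibonacci as described previously".
- **DLT/AE subsection.** This covers the case where no exposure data exist and also a second case: "if the exposure does not fall below the limits described above, initial dose escalations will be in increments of up to 2-fold". That ceiling lasts until a DLT or listed AE is seen. If a listed event occurs, modified Fibonacci begins and "the next immediate escalation increment will be a maximum of 67% of the current dose", followed by 50%, 40% and 33%. Separately, "A modified Fibonacci based escalation will be triggered after dose level 4 and no further 2 fold increase in dose will be employed thereafter".
- **Appendix 3.** If the criteria hold for a dose beyond a 2-fold step, that dose may be chosen; "otherwise, the next dose will default to 2-fold increase".

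Section 3.1.1.1 also says that the increments are set out in Figure 3.1.1.1-2, which is not reproduced in the text available for review. SAP Section 5 mentions the transition from 2-fold to modified Fibonacci steps but gives no increments, so it does not settle the matter.

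**The concern.** The three texts meet in one state: PK data are available, the safety-margin criterion is not met, no DLT or listed AE has occurred, and the step falls before the dose-level-4 cap. The exposure subsection makes nearness to the margin a sufficient reason to move to modified Fibonacci. The DLT/AE subsection leaves nearness off its list of events that start modified Fibonacci and keeps 2-fold available. Appendix 3 makes 2-fold the default. The exposure check therefore limits the step to 67% in one place and only removes steps larger than 2-fold in the others.

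This is a first-in-human study, the first three cohorts may hold only 1 to 2 subjects, and Section 7 provides no data monitoring committee. Two people applying different paragraphs could each justify a different next dose, and the difference would arise as exposure approaches the limit that the protocol itself names.

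**Working it through.** **Side-by-side reading of the state described above**

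- Exposure subsection: modified Fibonacci, so at most +67%.
- DLT/AE subsection: up to 2-fold, so at most +100%.
- Appendix 3, decision rule: 2-fold by default, so +100%. Its opening paragraph differs again: it says that a new dose will be calculated from PK data if the criteria are not met.

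Two wording gaps add to this. The word *near* is not defined. The exposure subsection also refers back to an earlier description of modified Fibonacci, but none precedes it in Section 3.1.1.1; the increments come afterwards.

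**Can the state arise before the cap?**

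Inputs from Appendix 3 and Section 3.1.1.1:

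- starting dose 3 mg, or 0.05 mg/kg at 60 kg
- projected exposure 79 µg•h/mL at that dose
- prior slope mean 1,580, with spread 316.2
- CV 30%
- margin 842 µg•h/mL
- criterion: 90% quantile below the margin (z = 1.2816)

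The plan's own figure reproduces: 79 / 0.05 = 1,580 per mg/kg.

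The predictive 90% quantile at dose d (mg/kg), before any PK data, is

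d × [1,580 + 1.2816 × √(316.2² + (0.30 × 1,580)²)] = d × [1,580 + 1.2816 × 569.8] = d × 2,310.

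The criterion fails above 842 / 2,310 = 0.364 mg/kg, or 21.9 mg at 60 kg. Appendix 3 does not say whether 316.2 is an SD or a variance. Read as a variance, the multiplier is 2,188 and the limit is 0.385 mg/kg, or 23.1 mg.

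Now take the 2-fold path 3, 6, 12 mg. The next step is to dose level 4, before the cap.

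- **2-fold:** 24 mg = 0.40 mg/kg. The 90% quantile is 0.40 × 2,310 = 924 (variance reading 875). Both exceed 842. Any dose beyond 2-fold is higher still and also fails, so Appendix 3 falls back on its 2-fold default.
- **67%:** 12 × 1.67 = 20.0 mg = 0.334 mg/kg. The 90% quantile is 0.334 × 2,310 = 772 (variance reading 731). Both are below 842.

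The state is therefore reachable, and on this path the two readings fall on opposite sides of the margin whichever way 316.2 is read. This shows that the conflict has practical content; it does not show which step is right.

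**The case against.** The strongest answer is that Figure 3.1.1.1-2 governs, since Section 3.1.1.1 says that the increments are explicitly described there. It may well favour one reading, so nothing firm can be said about what sites would do with the figure in hand. It cannot make the written sentences agree, and Section 3.1.1.1 also describes it as a summary of the rules.

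Second, 2-fold is a ceiling in the DLT/AE subsection, so a step of 67% or less satisfies both subsections. That is correct. The permitted maxima still differ, and Appendix 3 states a default and not a ceiling.

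Third, the exposure subsection's reference to mTPI and modified Fibonacci could be shorthand for the whole toxicity-guided scheme, with 2-fold steps first and Fibonacci later. The synopsis and Section 3.1.1.1 do speak of a transition from 2-fold to modified Fibonacci. This is plausible, but the wording does not compel it.

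Several stronger readings are tempting, and the documents do not support them:

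- A reader might infer that exposure-guided 3-fold steps continue after dose level 4, because the exposure subsection mentions cohort 4 and later cohorts. Those words sit in a parenthesis about cohort size, and the DLT/AE subsection expressly imposes modified Fibonacci after level 4.
- A reader might infer that this rule sets every dose. It does not: mTPI decides whether to escalate, toxicity is considered before exposure, and the mismatch needs all four conditions at once.
- A reader might infer that the differing AE wordings are separate triggers. They can be read as shorthand for the listed events.
- A reader might extend the illustration to a path of 3, 9, 18 mg. There a 67% step to about 30 mg (0.50 × 2,310 = 1,155) and a 2-fold step to 36 mg (0.60 × 2,310 = 1,386) both fail the criterion, so that path does not put the readings on opposite sides of the margin.

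**Conclusion.** The conflict holds as the text is written, within a narrow state: PK available, safety-margin criterion not met, no DLT or listed AE, and before the dose-level-4 cap. There the maximum increment is 67% in one sentence and 100% in two others. On the 3, 6, 12 mg path the difference is about 20 mg against 24 mg for the next dose, with 90% exposure quantiles of about 770 and 924 against 842.

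Those figures rest on Appendix 3's prior with no PK data yet, a 60 kg subject, linear PK, and 2-fold steps up to 12 mg. They compare an AUC(0-∞) model with an AUC(0-168h) margin, as Appendix 3 does. Accrued PK data would move them. The textual conflict depends on none of these assumptions. The documents do not establish that either increment is the intended one, or that either is unsafe.

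**What to change.** Reconcile the exposure subsection and the DLT/AE subsection of Section 3.1.1.1 with Appendix 3, including its opening paragraph. The state with PK available, the safety-margin criterion not met and no DLT or listed AE should have one maximum increment and one defined trigger. Replace *near* with the criterion that is meant, correct the backward reference to modified Fibonacci, and check that Figure 3.1.1.1-2 says the same. The AE-trigger wording can be aligned in the same edit. The choice of increment is for the sponsor and investigators; none is proposed here. The cost is a wording amendment, with no additional subjects or procedures.

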3.1.1.2 BMS-986183 and Nivolumab Dose Escalation (Part 3)

Dose escalation with BMS-986183 and nivolumab combination therapy will follow the same guidelines as described in Section 3.1.1.1. An mTPI design similar to that described for BMS-986183 monotherapy (see Section 3.1.1.1) will guide dose-escalation decisions. A total of approximately 21 evaluable subjects will be treated across 4 dose levels (3 to 6 subjects for each dose level). Additional subjects may be treated if additional dose levels are required as described in "Selection of Dose Levels" below.

Selection of Dose Levels to be Evaluated

The starting dose of BMS-986183 to be combined with nivolumab at 360 mg Q3W will be at least 1 dose level below the dose that is currently considered tolerated in BMS-986183 dose escalation (Part 1) of this study (Combination Dose Level 1). The subsequent combination doses will not exceed the monotherapy dose currently considered tolerated.

Approximately 21 subjects will be enrolled in ascending dose cohorts starting with a dose of BMS-986183 (Combination Dose Level 1) with nivolumab 360 mg administered Q3W in a 21-day

cycle. Subsequent escalation to Combination Dose Level 2 and onward (or MTD determined from BMS-986183 dose escalation [Part 1]) in combination with nivolumab 360 mg Q3W will be guided by the mTPI design described below. In the event that the first dose level of BMS-986183 is determined to exceed the MTD in combination with 360 mg Q3W of nivolumab, a lower BMS-986183 dose tested in monotherapy escalation may be explored based on available safety, PK, and biomarker information. Nivolumab will be administered as 360 mg IV Q3W in all dose cohorts.

Intermediate doses of BMS-986183 in combination with nivolumab 360 mg Q3W may be evaluated if agreed upon by the BMS Medical Monitor and investigators. The next dose level will not exceed 100% of the dose increment.

No intra-subject dose escalation of BMS-986183 or nivolumab is allowed at any dose level.

Dose Escalation Decision Guide

As in BMS-986183 dose escalation (Part 1), an mTPI design (Table 3.1.1.2-1) will be used to guide dose-escalation decisions and to select the MTD. A DLT target rate of 29% (EI = [27%, 31%]) will be used for combination therapy to guide escalation decisions. Dose-escalation decisions will be based on the total number of subjects in a dose level who are DLT evaluable and the number of DLTs observed at that dose level, guided by the mTPI Bayesian model and posterior inference.

The number of subjects in the initial cohort of each dose level will be 3 to 4. The fourth subject may be enrolled following agreement between the investigator and the Sponsor/Medical Monitor if able to start the first day of dosing within approximately 1 week of the third subject in the same dose-escalation cohort. The DLT evaluation period will be 21 days. See Section 4.5.1 for further details of DLT evaluation. Enrollment of additional cohorts at the same dose level will proceed in sample sizes of up to 3 or 4 subjects. Subsequent dose levels will follow similar cohort enrollment size and decision rules. At least 3 DLT evaluable subjects at each of the dose levels in BMS-986183 and nivolumab dose escalation (Part 3) will be required to enable a decision to escalate, add more subjects to the current dose level, or de-escalate and declare the current dose as unacceptable (ie, exceeding the MTD). Subjects with insufficient data to establish safety during the DLT evaluation period at a dose level may be replaced upon agreement of the BMS Medical Monitor and investigators.

Dose Selection for BMS-986183 and Nivolumab Dose Expansion (Part 4)

At the end of the BMS-986183 and nivolumab dose-escalation period, the cumulative number of subjects who experience a DLT at each dose level will be used to estimate the MTD of BMS-986183 in combination with nivolumab using isotonic regression. The MTD will be selected as the dose level with the smaller difference of estimated toxicity rate and the target DLT rate among the dose levels explored.

Once the safety (during DLT evaluation) of a dose level has been determined, additional subjects may be added at that dose to better characterize the PK, safety, and pharmacodynamic profile or to satisfy regional/local requirements (eg, in Chinese subjects where weight or genetic factors may play a role in safety, PK, and pharmacodynamics).

3.1.2 Dose Expansion (BMS-986183 Dose Expansion [Part 2] and BMS-986183 and Nivolumab Dose Expansion [Part 4])

